Other statistics (e.g., CIs) will be presented using the same general rules outlined above or assessed for the most appropriate presentation based on the underlying data.

Unless noted otherwise, statistical significance testing will be two-sided and performed using α =0.05. Confidence intervals (CIs) will be calculated at the 95% level, reflecting a type I error rate of 0.05. P-values will be reported for all statistical tests, rounded to four decimal places. P-values less than 0.0001 will be displayed as "<0.0001"; p-values greater than 0.9999 will be displayed as ">0.9999".

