7.1.1.3 Hypotheses and Test

The following hypothesis for the primary efficacy variable regarding the proportion of patients with a \geq 2-step improvement from baseline in DRSS score in the study eye at week 48 will be conducted to demonstrate the superiority of the KSI-301 group compared to the sham group.

The hypothesis to be tested is:

 $H_0: p_k - p_s = 0 \qquad \qquad vs \qquad H_1: p_k - p_s \neq 0$

Where p_k and p_s are the true proportions of patients with a ≥ 2 -step improvement from baseline in DRSS score in the study eye at week 48 in the KSI-301 and sham groups, respectively. The primary efficacy endpoint will be tested at the significance level of $\alpha = 0.0498$.

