7.1.2 Analysis of Primary Efficacy Endpoint

The primary efficacy endpoint will be estimated based on the FAS, i.e., all randomized subjects who received at least one treatment injection and have gradable DRSS value at baseline.

The statistical analysis will be performed using the Cochran-Mantel-Haenszel (CMH) method,

A 'Hypothetical' strategy will be applied for all intercurrent events where measurements after occurrence of intercurrent event will be imputed using the last observation carry forward (LOCF) procedure. For patients who develop sight-threatening complication(s) and have non-gradable value at their first visit where open-label treatment is administered, the non-gradable values will be imputed as no change from baseline. For patients without intercurrent event, missing and non-gradable values at Week 48 will be imputed using LOCF. Baseline will be carried forward if all post-baseline observations are missing or non-gradable. Non-gradable values are observations where DRSS level is 90.

The p-value will be reported for comparison between KSI-301 and sham groups. In addition, the weighted percentages difference between the KSI-301 and sham (i.e., KSI-301 – sham) and 95.02% CI of the difference will be presented. Percentages are calculated as 100×number of "responders"/number of patients in FAS. Weighted percentages are based on weighted average of observed estimates across strata using CMH weights. The CI are based on the normal approximation to the binomial proportions.

The CMH method as described for the primary efficacy analysis will be used for all sensitivity analyses below.

7.1.3 Sensitivity Analysis 1

In this analysis, a 'Composite' strategy will be applied for all intercurrent events where patients with occurrence of intercurrent event by Week 48 will be considered as non-responders. For patients without intercurrent event, missing and non-gradable values at Week 48 will be imputed using LOCF, and baseline will be carried forward if all post-baseline observations are missing or non-gradable as in the primary analysis.

7.1.4 Sensitivity Analysis 2

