7.2.2 Proportion of Eyes Improving ≥3 Steps on DRSS

The second key secondary efficacy endpoint of interest is proportion of eyes improving ≥ 3 steps on DRSS from baseline at Week 48. The same intercurrent events and analysis method from the primary efficacy endpoint will be used. See Sections 7.1.1.4 and 7.1.2.

A sensitivity analysis for this key secondary efficacy endpoint will be performed where patients with baseline DRSS level outside of levels 47 and 53 will be excluded from the analysis.

7.2.3 **Proportion of Eyes Developing PDR**

The third key secondary efficacy endpoint of interest is the proportion of eyes developing PDR from baseline through Week 48. The same intercurrent events and analysis method from the first key secondary efficacy endpoint will be used. See Section 7.2.1.

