7.3 Additional Secondary Efficacy Analyses

As specified in Section 4.0, the Primary Analysis will evaluate the efficacy of KSI-301 compared to sham from Day 1 up to Week 48.

Table 4 lists the additional secondary efficacy endpoints, efficacy variable derivations, reporting statistics and analysis methods for the Primary Analysis and until the end of study.

Binary secondary efficacy endpoints will utilize the Cochran-Mantel-Haenszel (CMH) method stratified by the randomization stratification factors (i.e. baseline DRSS level and HbA1c level).

Time to event endpoints will be analyzed using the Kaplan-Meier estimates. The number of observations censored will be provided for each treatment group. The 50th percentile of Kaplan-Meier estimates will be used to estimate the median time to first event in each treatment group. A 2-sided 95% CI will be provided for the estimates. A log-rank test stratified by the randomization stratification factors (i.e. baseline DRSS level and HbA1c level) will be performed to compare the survival distributions between the treatments. The hazard ratio and its 95% CI will be reported from a Cox regression model stratified by the same randomization stratification factors with treatment as the covariate. For patients not known to have had an event at the time of the analysis data cutoff, the time will be censored at the date of the last scheduled study visit at analysis data cutoff.

Continuous endpoints (e.g. mean change from baseline in BCVA) will utilize a Mixed Model for Repeated Measures (MMRM). The model assumes missing at random (MAR). The model will include the change from baseline value as the dependent variable; categorical covariates of treatment group, protocol scheduled visit, treatment × visit interaction, and the randomization stratification factors (i.e. baseline DRSS level and HbA1c level) as well as continuous covariate of baseline BCVA, as fixed effects; and then subject as a random effect. Within-subject correlations will be assumed to follow an unstructured covariance matrix. If the model assuming an unstructured covariance matrix does not converge, a heterogeneous compound symmetry structure or an AR(1) covariance structure will be fitted.

For all additional secondary efficacy endpoints, data after the occurrence of intercurrent event will be censored, and missing and non-gradable data will not be imputed. Only observed, gradable and non-censored data will be used for analysis.

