Additional Secondary Efficacy Endpoint	Variable Derivation [Source]	Summary Statistics [Analysis Set]	Method of Analysis		
Proportion of eyes developing PDR or ASNV from baseline through Week 48	Binary endpoint: patients developed PDR or ASNV (yes/no) [Sight-threatening Complication/EDC]				
Proportion of eyes developing vitreous hemorrhage or tractional retinal detachment, believed to be due to PDR, from baseline through Week 48	Binary endpoint: patients developed vitreous hemorrhage or tractional retinal detachment believed to be due to PDR (yes/no) [Sight-threatening Complication/EDC/Review of AEs]				
Proportion of eyes developing DME from baseline through Week 48	Binary endpoint: patients developed DME (yes/no) [Sight-threatening Complication/EDC]	Difference in proportions (%) and 95% CI at each time point [FAS], up to Week 48	CMH method adjusting for randomization stratification factors (similar to Section 7.1.2)		
Proportion of eyes with a ≥ 2 - step or a ≥ 3 -step worsening on DRSS from baseline at Week 48	Binary endpoints: patients with a ≥2-step worsening in DRSS (yes/no); patients with a ≥3-step worsening in DRSS (yes/no);				
Proportion of eyes who lose ≥ 5 , ≥ 10 , or ≥ 15 letters in BCVA from baseline by visit over time	Binary endpoints: patients had a BCVA loss \geq 5 (yes/no); patients had a BCVA loss \geq 10 (yes/no); patients had a BCVA loss \geq 15 (yes/no). [Visual Acuity Score/EDC]				
Time to first development of PDR, ASNV, or DME through Week 48	Time to event endpoint: Time from first treatment to development of PDR, ASNV, or DME (in months) [Sight-threatening Complication/EDC]				

Table 4: Additional Secondary Efficacy Endpoints and Analysis Methods

KS301P106 SAP Version 0.1 KSI-301 – Kodiak Sciences Inc.

Additional Secondary Efficacy Endpoint	Variable Derivation [Source]	Summary Statistics [Analysis Set]	Method of Analysis			
Time to first development of PDR or ASNV through Week 48Time to event endpoint: Time from first treatment to development of PDR or ASNV (in months) [Sight-threatening Complication/EDC]						
Time to first development of vitreous hemorrhage or tractional retinal detachment, believed to be due to PDR through Week 48	to first development of us hemorrhage or onal retinal detachment, red to be due to PDR gh Week 48		Kaplan-Meier and Cox regression model stratified by randomization stratification factors (Section 7.3)			

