Appendix 2: Sample SAS Code

For stratum *i* (i = 1, 2, ..., K), let

 n_{ii} = number of subjects with treatment j (j = 0, 1)

 x_{ii} = number of responders with treatment j

 $n_i = n_{i0} + n_{i1} =$ total number of subjects

 $\hat{p}_{ii} = x_{ii} / n_{ii}$ = observed proportion of responders with treatment *j*

 $\overline{p}_i = \frac{n_{i0}\hat{p}_{i0} + n_{i1}\hat{p}_{i1}}{n_{i0} + n_{i1}} = \text{pooled observed proportion of responders combining the}$

two treatments

 $\hat{\delta}_i = \hat{p}_{i1} - \hat{p}_{i0}$ = observed difference in proportions of responders between the two treatments

$$w_{i} = \frac{\frac{n_{i0}n_{i1}}{n_{i0} + n_{i1}}}{\sum_{j=1}^{K} \frac{n_{j0}n_{j1}}{n_{j0} + n_{j1}}} = \text{Cochran-Mantel-Haenszel (CMH) weight}$$

(Cochran 1954; Mantel and Haenszel 1959).

Estimates

The overall proportion of responders with treatment j will be estimated by the weighted average of the observed proportions over the strata for treatment j using the CMH weights,

$$\hat{p}_{\scriptscriptstyle wj} = \sum_{\scriptscriptstyle i=1}^{\scriptscriptstyle K} w_{\scriptscriptstyle i} \hat{p}_{\scriptscriptstyle ij}$$
 ,

with estimated variance

$$\hat{V}(\hat{p}_{wj}) = \sum_{i=1}^{K} w_i^2 \frac{\hat{p}_{ij}(1-\hat{p}_{ij})}{n_{ij}}.$$

The overall difference in proportions of responders between the two treatment groups (treatment 1 vs. treatment 0) will be estimated using the weighted average of the observed differences in proportions between the two treatment groups over the strata using the CMH weights,

$$\hat{\delta}_{w} = \sum_{i=1}^{K} w_{i} (\hat{p}_{i1} - \hat{p}_{i0}),$$

with estimated variance

$$\hat{V}(\hat{\delta}_w) = \sum_{i=1}^K w_i^2 \, \hat{V}(\hat{\delta}_i) \,,$$

where

$$\hat{V}(\hat{\delta}_{i}) = \frac{\hat{p}_{i0}(1-\hat{p}_{i0})}{n_{i0}} + \frac{\hat{p}_{i1}(1-\hat{p}_{i1})}{n_{i1}}$$

(Cochran 1954; Mehrotra and Railkar 2000).

Two-Sided (1-α) 100% Confidence Interval

The two-sided $(1-\alpha)$ 100% confidence interval for the overall proportion of responders with treatment *j* will be calculated as

$$\hat{p}_{wj} \pm z_{a/2} \sqrt{\hat{V}(\hat{p}_{wj})} \,.$$

The two-sided $(1-\alpha)$ 100% confidence interval for the overall difference in proportions of responders between treatment 1 and treatment 0 will be calculated as

$$\hat{\delta}_{_{\boldsymbol{W}}} \pm \boldsymbol{z}_{_{a/2}} \sqrt{\hat{V}(\hat{\delta}_{_{\boldsymbol{W}}})}$$
 ,

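### The planned confidence interval for differences in proportions is an unpooled Wald interval; if few eyes gain ≥3 DRSS steps and the arms differ, it covers about 87–93% rather than 95.02%

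*SAP*

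**What the plan says.** SAP 7.1.2 analyses the primary endpoint by the CMH method and reports the weighted difference, KSI-301 minus sham, with an interval: "95.02% CI of the difference will be presented". The level matches the two-sided alpha of 0.0498 in SAP 7.1.1.3. On construction the section says only: "The CI are based on the normal approximation to the binomial proportions".

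Appendix 2 gives the formula: "The overall difference in proportions of responders between the two treatment groups (treatment 1 vs. treatment 0) will be estimated using the weighted average". What is averaged is the set of stratum differences, with CMH weights. The variance sums unpooled p(1−p)/n terms for each arm within each stratum, and the limits are the estimate plus or minus z times the square root of that variance. No score, exact or other small-count alternative appears in the SAP text available.

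The method is carried to other endpoints. For ≥3-step improvement, SAP 7.2.2 says: "The same intercurrent events and analysis method from the primary efficacy endpoint will be used". For the additional binary secondary endpoints, SAP Table 4 specifies the "CMH method adjusting for randomization stratification factors (similar to Section 7.1.2"), with a 95% interval.

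**The concern.** The unpooled Wald variance is estimated from the observed proportions. An arm or stratum cell with no responders contributes zero variance, and one with very few contributes too little. When counts are low and the arms differ, the interval is therefore too short and too symmetric.

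≥3-step improvement is the endpoint most exposed. On the abbreviated scale in protocol Table 1, an eye at level 47 must reach level 20 and an eye at level 53 must reach level 35. SAP 7.1.2 also imputes some ungradable values as no change and carries baseline forward when nothing later is usable, and both rules make the eye a non-responder. A near-zero sham rate is a case worth planning for, although nothing in the documents establishes it.

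At stake is the stated confidence of an interval that will be reported beside a confirmatory p-value, and its agreement with that p-value.

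**Working it through.** **Inputs from the documents.** 120 per arm (SAP 9.0). Alpha 0.0498 (SAP 7.1.1.3), so the level is 1 − 0.0498 = 95.02%, which reproduces the plan's figure; z = 1.9617. Stratification by baseline DRSS and HbA1c level (SAP 7.3).

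**Assumptions.** Two levels per factor, following the SAP Table 2 subgroups, hence 4 strata; stratum sizes 47/37/20/16 in each arm; the same responder rate in every stratum; the ≥3-step rates shown below.

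**Formula (Appendix 2).** With equal arms in stratum i, w_i = n_i/120, and

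V = Σ w_i² [p_i1(1−p_i1) + p_i0(1−p_i0)]/n_i; interval = Σ w_i(p_i1 − p_i0) ± 1.9617·√V.

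**Hand check, ignoring strata, true rates 3% versus 0%.** Sham contributes nothing.
- 0 responders on KSI-301: the interval is 0 to 0. Probability 0.97^120 = 2.6%.
- 1 responder: upper limit 0.833 + 1.9617 × 0.830 = 2.46 percentage points (pp), below the true 3. Probability 120 × 0.03 × 0.97^119 = 9.6%.

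The interval therefore lies below the truth in 2.6 + 9.6 = 12.2% of trials before any other miss is counted.

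**Coverage (%).** The stratified results are from at least 200,000 simulated trials per row; the unstratified Wald results are exact enumeration.

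| KSI-301 vs sham | Stratified Wald | Unstratified Wald | Interval below / above truth | Interval excludes 0, CMH not significant |
|---|---|---|---|---|
| 3% vs 0% | 87.4 | 87.5 | 12.2 / 0.4 | 0 |
| 5% vs 0.5% | 92.1 | 92.1 | 6.8 / 1.1 | 2.5 |
| 5% vs 1% | 91.7 | 92.3 | 6.9 / 1.4 | 3.7 |
| 10% vs 1% | 93.1 | 93.3 | 5.4 / 1.5 | 1.5 |
| 10% vs 0% | 92.1 | 95.4 | 6.3 / 1.6 | 0 |

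The unstratified interval does almost as badly in four of the five rows, so the main cause is the Wald approximation; sparse strata add to it at 10% versus 0%. Equal strata (30 each), uneven strata (60/40/12/8) and 8 strata change the first four rows by no more than about 0.2 points. With 4 strata of 50/30/25/15, a 40-point grid (sham 0–1%, KSI-301 2–10%) gives coverage of 85.4% to 94.2%, median 92.4%, and disagreement with CMH of up to 4.35% (6% versus 1%).

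**Where there is little or no problem.** 94.0% at 15% versus 1%; 94.3% at 20% versus 1%; 95.1% at 2% versus 2%; 98.0% at 1% versus 1%. For rates of the kind the primary endpoint may show: 94.5% at both 40% versus 5% and 26% versus 10%.

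**One data set: 8/120 (5, 1, 2, 0 by stratum) versus 2/120 (0, 1, 1, 0).**
- Difference: (8 − 2)/120 = 5.00 pp.
- Since w_i²/n_i = n_i/120², V = [5(42/47) + 2 × 1(36/37) + 2(18/20) + 1(19/20)]/120² = 9.164/120², so √V = 2.523 pp.
- Planned interval: 5.00 ± 1.9617 × 2.523 = 0.05 to 9.95 pp, which excludes zero.
- CMH: numerator (2.5 + 0 + 0.5)² = 9; variance 5·89/(4·93) + 2·72/(4·73) + 3·37/(4·39) = 2.401; chi-square 9/2.401 = 3.749; p = 0.053, not significant.
- Stratified Miettinen-Nurminen: −0.08 to 11.19 pp, in line with the test.

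If neither arm has a responder, the planned interval has zero width; the score interval is about ±3.2 pp.

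**Coverage of the alternative.** Stratified Miettinen-Nurminen (100,000 trials): 98.7% at 3% versus 0%, 96.5% at 5% versus 0.5%, 95.7% at 10% versus 1%, 95.9% at 10% versus 0%, 95.5% at 2% versus 2%, 95.1% at 40% versus 5%.

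**The case against.** The strongest reply is that the shortfall rests on assumed rates. It needs roughly 0–1 sham responders in 120 and a modest KSI-301 rate. At 2% in sham, coverage is already 94.2% (against 5%) and 94.4% (against 8%). The 87% figure comes from the most extreme of the five tabulated scenarios; the others fall short by about 2–3 points. This stands, and the point is conditional for that reason.

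Second, no decision changes, and the errors fall mainly where no claim would be made. In the first three rows of the table, virtually all misses below the truth occur in trials where CMH is not significant. Among significant trials, coverage is 99.3%, 98.2%, 96.7% and 97.1% in the first four rows; only 10% versus 0% stays low, at 92.3%. Most misses understate the benefit. All of this is correct. However, a confidence level is stated for the interval whether or not the test succeeds, and a non-significant result is when readers look to the upper limit to see what benefit remains possible.

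Third, scope. The method also serves the complication endpoints in SAP 7.2.1 and 7.2.3, for which no shortfall has been shown. The Table 4 endpoints are not imputed after intercurrent events, so their denominators may be below 120; they were not simulated as such. The score interval is also off nominal at the rarest rates, though on the conservative side.

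**Conclusion.** The point holds as a conditional, low-priority one. The interval is a stratified unpooled Wald interval. If sham has about 0–1% ≥3-step responders and KSI-301 a few percent, its coverage is mostly 87–93% (full range about 85–94%) against a stated 95.02%, with the upper limit too low in most misses. It can also exclude zero beside a non-significant CMH p-value, in up to about 4% of trials with 4 strata. The rates and stratum sizes are assumptions; the result is sensitive to the rates and hardly at all to the strata. Type I error, the testing hierarchy and the primary endpoint interval are not at issue.

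**What to change.** In SAP 7.1.2, 7.2 and Appendix 2, specify a stratified Miettinen-Nurminen score interval, or a stratified Newcombe interval, with the same CMH weights and confidence level. Apply it at least to ≥3-step improvement (7.2.2) and to those Table 4 binary endpoints expected to have few events. List these endpoints by name before unmasking, so that the choice cannot depend on the data. Keep the CMH-weighted point estimate and the CMH p-value. The primary endpoint interval can stay as it is; using the score interval there too would avoid having two methods.

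The cost is a few lines of SAP text and programming, with no cost in data or alpha. Intervals become slightly wider, and conservative at very low rates (98.7% coverage at 3% versus 0%).

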9.4.1 General Considerations

At Day 1, participants will be randomized 1:1 into one of two treatment arms:

- Group A: KSI-301 5 mg via intravitreal injection at Day 1, Week 8, Week 20, and every 24 weeks thereafter through Week 92.
- Group B: Sham injections at Day 1, Week 8, Week 20, and every 24 weeks thereafter through Week 92.

CONFIDENTIAL

This study is divided into two efficacy and safety assessment periods (Section 1.2), as follows:

- Year 1: from baseline to Week 48; and
- Year 2: from Week 52 to Week 100.

At Week 48, the primary endpoint (the proportion of eyes improving ≥ 2 steps on DRSS from baseline at Week 48) will be compared between the KSI-301 5 mg treatment group and sham using the CMH method

Missing values post-baseline will be imputed using the last observation carried forward (LOCF) procedure. If a participant develops a sightthreatening complication due to DR (DME, PDR, or ASNV), a color fundus photograph for DRSS grading will be obtained and submitted to the reading center at the time of diagnosis, and DRSS scores collected subsequently will be censored. Baseline will be carried forward if all post-baseline observations are missing.

Analysis of data for the first period of the study will be performed when all participants have either completed the Week 48 visit or have discontinued from the study, all data have been entered into the database, cleaned, and verified as appropriate, and the database has been locked.

Likewise, analysis of data for the second period of the study will be performed when all participants have either completed the Week 100 visit or have discontinued from the study, all data have been entered into the database, cleaned, and verified as appropriate, and the database has been locked.

Details of all preplanned analyses, including alternative imputation approaches for the handling of missing data, subgroup analyses (for example, across key demographic and ocular baseline characteristics), and sensitivity analyses, will be included in the SAP. The results of all analyses detailed in the SAP will appear in the final clinical study report.

9.4.2 **Primary Endpoint(s)**

Unless stated otherwise, all analyses described will be performed on the ITT population.

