7.1.1.4 Intercurrent Events

The following intercurrent events (ICEs) may impact the assessment of the primary efficacy endpoint:

- 1. Treatment misallocation at 1 or more study visits.
- 2. Use of prohibited medications in the study eye.
- 3. Development of sight-threatening complication(s) and initiation of open-label KSI-301 5 mg treatment, panretinal photocoagulation, or other treatment for DME, ASNV, and/or PDR.
- 4. Premature discontinuation from study treatment due to study eye adverse events or due to lack of efficacy.
- 5. Premature discontinuation from study treatment due to events unrelated to study treatment such as malignancies, systemic infections, trauma, or other systemic adverse events that are not treatment-related, including discontinuations due to COVID-19.

Intercurrent events will be classified by the Sponsor prior to treatment code unmasking to prevent potential bias. Intercurrent events and the time to intercurrent events will be tabulated and listed by treatment group. Strategies for addressing the potential impact of these intercurrent events are described below.

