This analysis will follow the same 'Hypothetical' strategy for handling of intercurrent events and analysis method as the primary analysis, with the exception that patients with the following significant protocol deviations will be excluded from the analysis: deviation from key inclusion/exclusion criteria as defined in Section 7.1.1.1, treatment misallocation at 1 or more study visits by Week 48, and use of prohibited medications in study eye at any point by Week 48.

7.1.5 Sensitivity Analysis 3

This analysis will follow the same 'Hypothetical' strategy for handling of intercurrent events and analysis method as the primary analysis, with the exception that patients with baseline DRSS level outside of levels 47 and 53 will be excluded from the analysis.

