7.2 Key Secondary Efficacy Analyses

The key secondary endpoints will be estimated based on the FAS, defined as in Section 5.4.1.

Together with the primary endpoint and the key secondary endpoints, this family of tests will be conducted hierarchically to maintain a familywise Type I error rate of 4.98%. Each test within this family will be conducted at the 4.98% level if the preceding test was significant at the 4.98% level.

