9.0 SAMPLE SIZE CONSIDERATIONS

A sample size of approximately 240 participants with a target enrollment of approximately 120 participants in each treatment group (1:1 ratio) was calculated using the following assumptions:

- Anticipated of participants with a ≥2-step improvement from baseline in DRSS score in the KSI-301 5 mg Q24W group versus in the sham group.
- Statistical power of $\geq 90\%$.
- Overall Type I error rate of 0.05.
- The statistical method used to compare the proportion with a ≥2-step improvement from baseline in DRSS score for the KSI-301 treatment group at Week 48 compared with sham will be the Cochran-Manzel Haenszel (CMH) method,

• Lost to follow-up/dropout rate of approximately

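### No sensitivity analysis of the primary endpoint changes the LOCF rule for participants who lack a Week 48 DRSS grade and have no listed intercurrent event

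*SAP*

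**What the plan says.** - **Primary analysis (SAP 7.1.2).** Grades after any intercurrent event are replaced by LOCF. Participants without an intercurrent event whose Week 48 grade is missing or non-gradable also get LOCF, and baseline is used if nothing gradable exists after baseline.
- **Sensitivity Analysis 1 (SAP 7.1.3).** Participants with an intercurrent event by Week 48 become non-responders. For everyone else the primary rule is repeated: "missing and non-gradable values at Week 48 will be imputed using LOCF, and baseline will be carried forward if all post-baseline observations are missing".
- **Sensitivity Analyses 2 and 3 (SAP 7.1.4 and 7.1.5).** Both open with the same sentence: "This analysis will follow the same 'Hypothetical' strategy for handling of intercurrent events and analysis method as the primary analysis". Analysis 2 then drops participants with key eligibility deviations, misallocation or prohibited medication. Analysis 3 drops those with baseline DRSS outside levels 47 and 53.
- **Intercurrent events (SAP 7.1.1.4).** Two of the five concern stopping study treatment. Event 4 covers study-eye adverse events and lack of efficacy. Event 5 covers events unrelated to treatment, such as malignancy, infection or trauma, "or other systemic adverse events that are not treatment-related, including discontinuations due to COVID-19".
- **Reasons for withdrawal (Protocol 7.1).** These include non-compliance, loss to follow-up, withdrawal of consent, and a decision by the investigator or sponsor.
- **Commitment (Protocol 9.4.1).** The SAP was to give details of all preplanned analyses, "including alternative imputation approaches for the handling of missing data".
- **Key secondary endpoint of at least 3 steps (SAP 7.2.2).** It takes over the primary endpoint's events and method. Its one sensitivity analysis excludes by baseline level.

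**The concern.** A sensitivity analysis for missing data should change the missing-data assumption. Here the assumption changes only for participants who have a listed intercurrent event. For those who simply leave, or whose Week 48 photograph cannot be graded, the primary analysis and all three sensitivity analyses use the same carried-forward grade. Agreement between the four results would then say nothing about whether the conclusion depends on that grade.

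At stake is the reading of the primary result and of the 3-step key secondary result. If few Week 48 grades are missing, the gap is harmless. If many are missing and the treatment effect is modest, the conclusion could rest on values not observed at Week 48, and no planned table would show it.

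**Working it through.** **Inputs.** Planned size is 240, or 120 per arm (SAP 9.0). The primary test is two-sided at 0.0498 (SAP 7.1.1.3), and the "95.02% CI of the difference will be presented" (SAP 7.1.2). These two agree: 1 − 0.9502 = 0.0498. The response rates and dropout behind the sample size are redacted, so the stated 240 can be neither reproduced nor faulted. All rates below are assumptions.

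**Step 1: apply the rules to example participants.** Baseline is level 53, improving to 43, which is two steps on the protocol's Table 1 (53 to 47 to 43).

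| Participant | Primary | Sens. 1 | Sens. 2 | Sens. 3 |
|---|---|---|---|---|
| Improved at Weeks 8 and 20, leaves, no listed event | responder | responder | responder | responder |
| Improved at Week 8 only (last grade), leaves, no listed event | responder | responder | responder | responder |
| Improved at Week 8, back to baseline at Week 20, leaves, no listed event | non-responder | non-responder | non-responder | non-responder |
| Improved at Week 20, leaves with a listed event | responder | non-responder | responder | responder |
| As row 1, with a deviation named in Sens. 2 | responder | responder | excluded | responder |

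Rows 1 and 2 are the gap. It needs no redacted figure.

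**Step 2: look for another analysis that fills it.** The SAP has no multiple imputation, tipping point or missing-as-non-responder analysis for this endpoint. MNAR appears only in the abbreviation list, and MAR is used only for the mixed model on continuous endpoints (SAP 7.3). The protocol's per-protocol set treated missing data as a deviation, but SAP 5.4 has no such set. The additional secondary analyses use observed data only (SAP 7.3), but the 2-step improvement endpoint is not among them. Subgroup analyses use the 7.1.2 method.

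**Step 3: what the choice could move.** One participant is 1/120 = 0.83 percentage points. Let m be the share of each arm without a Week 48 grade and without a listed event, and rK and rS the carried-forward response among them on KSI-301 and sham. LOCF and counting them as non-responders then differ by m × (rK − rS):

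- m = 1%, rK = 60%, rS = 0: 0.01 × 0.60 = 0.6 points
- m = 2%, rK = 60%, rS = 0: 0.02 × 0.60 = 1.2 points
- m = 5%, rK = 30%, rS = 5%: 0.05 × 0.25 = 1.25 points
- m = 15%, rK = 60%, rS = 0: 0.15 × 0.60 = 9.0 points

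This is the gap between two assumptions, not the bias of LOCF. Counting all of these participants as non-responders is itself an extreme.

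**Step 4: effect on the test.** Unstratified pooled two-proportion z-test, 120 per arm. For scale, 120 evaluable per arm gives 90% power for about 26.0% v 10%.

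| LOCF result | Missing per arm | Carried responders removed (KSI-301 / sham) | Difference | p |
|---|---|---|---|---|
| 30% v 10% | 10% (12) | 6 / 1 | 20.0 to 15.8 | 0.0001 to 0.0011 |
| 25% v 10% | 10% (12) | 6 / 1 | 15.0 to 10.8 | 0.0022 to 0.017 |
| 25% v 10% | 15% (18) | 13 / 2 | 15.0 to 5.8 | 0.0022 to 0.15 |
| 45% v 10% | 15% (18) | 13 / 2 | 35.0 to 25.8 | still about 0.000001 |

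Row 2 worked: 30 and 12 responders become 24 and 11, and 24/120 − 11/120 = 20.0% − 9.2% = 10.8 points.

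With sham unchanged, the number of KSI-301 responders that must be reclassified before p reaches 0.0498 is 8 (25% v 10%), 10 (20% v 5%), 14 (30% v 10%) or 32 (45% v 10%).

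**The case against.** **The direction of bias is not established.** A reader might infer that LOCF favours KSI-301, because someone who leaves after Week 32 is scored on a grade 12 weeks after the Week 20 dose but would be 28 weeks past it at Week 48 (48 − 20). The documents do not support that as a general claim. Completers are 4 weeks past the Week 44 dose at Week 48, as a leaver who had continued would have been. Someone who leaves after Week 44 carries a grade about 24 weeks past the Week 20 dose. Early-termination visits include fundus photographs, and with no gradable post-baseline value the participant is a non-responder. This objection stands; it is a reason to test the assumption.

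**The gap is narrower than it may look.** A reader might infer that every early improver who leaves is a responder in every planned analysis. That is too broad. The improvement must still be present at the last gradable visit. Sensitivity Analyses 2 and 3 can exclude the person. An early-termination grade mapped to the Week 48 window (Days 323 to 364, SAP 5.8) counts as observed. Event 5 is also open-ended, and the sponsor classifies events before unmasking, so some leavers may be treated as having an event. All of this limits the group without removing it.

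**Stopping treatment is not leaving the study.** A reader might call Sensitivity Analysis 1 inverted, because a stop for trauma counts as failure while a stop for a treatment-related systemic adverse event fits neither event 4 nor event 5. But Protocol 7.1 keeps people who stop treatment in the study. If the second person has a Week 48 grade, responder status rests on real data. The point holds only where the grade is missing.

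**The SAP overrides the protocol.** SAP 10.0 gives its missing-data strategies and sensitivity analyses precedence, and primary LOCF matches Protocol 9.4.1. Both are true. But SAP 1.0 says changes from the protocol will be explained in Section 10.0, and that section does not explain why no alternative imputation is given for these participants.

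**Conclusion.** The point holds in this form. With no observed gradable Week 48 DRSS, no listed intercurrent event, and at least 2 steps of improvement at the last gradable visit, a participant is a responder in the primary analysis and in every sensitivity analysis of that endpoint that includes them. No planned analysis varies the missing-data assumption for this group, although the protocol said alternatives would be provided. The 3-step key secondary endpoint has the same gap.

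The structural finding rests on the text alone. The direction and size of any LOCF bias are unknown. The firm figure is 0.83 points per participant at 120 per arm. Under the assumed rates, the gap between LOCF and non-responder counting runs from under 1 point to 9 points, and the consequence from negligible to loss of significance.

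This is a gap in the sensitivity analyses. It does not show that the primary analysis is wrong or that its result would be overturned.

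**What to change.** Leave the primary analysis and the intercurrent-event list as they are.

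1. **Sensitivity Analysis 1 only:** after the SAP 5.8 windowing, count every FAS participant without an observed gradable Week 48 DRSS as a non-responder, whatever the reason. Participants with a listed event remain non-responders, as now.
2. **3-step key secondary endpoint:** add the same rule as a sensitivity analysis.
3. **Alternative imputation:** add one table for missing Week 48 responder status, by multiple imputation or as a tipping-point analysis over the assumed response among the missing.

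Do not widen events 4 and 5 to cover stopping treatment for any reason. SAP 7.1.2 replaces grades after an intercurrent event with LOCF, so widening would discard observed Week 48 grades from people who stop treatment but stay in the study. It would also censor their later data in the additional secondary analyses (SAP 7.3).

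The cost is some SAP wording and a few extra tables from data already collected. The sensitivity estimate may be less favourable than the one now planned.
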